# Part 2 (MRD)

	Screening	Check-in	Treatment	Washout	Treatment	Check-out	Early	Follow-up Visit
	Dave -28	CIICK-III	Treatment	washout	Treatment	Check-out	Termination	Day 17
Study Day:	to -2	Day -1	Day 1	Day 2	Day 3-9	Day 10	(a)	(±2) (b)
Confinement		X	X	Х	X	Х		
Informed consent	Х							
Inclusion/exclusion	Х	Х						
criteria								
Demographics and	Х	Х						
medical history								
Medication history	Х							
Physical examination	Х		X (c)	Х	X	Х	X	
Vital signs (d)	Х	Х	Х	Х	Х	Х	Х	Х
Weight, height, and	Х	Х				Х	Х	
BMI (e)								
Concurrent medical	Х	Х						
conditions								
Concomitant	Х	Х	X	Х	X	Х	X	Х
medications (f)								
Clinical laboratory	Х	X		Х	X	X	X	X (s)
tests (g)								
Hepatitis panel	Х							
HIV screening	Х							
TB screening	Х							
Pregnancy test (hCG)	Х	X				X	X	
(h)								
Urine	Х	X						
drug/alcohol/cotinine								
Screen	37	V	V	N/	N/	V	N/	
ECG (1)	X	X	X	X	X	X	X	
Telemetry (j)			X		X			
PGx DNA sample			X					
DCu DNA secondo			v		V			
rollection (1)			А		A .			
PK blood collection			v	v	v	v	v	
(m)			Λ	Λ		Λ		
PK urine collection			x	X	x	X	X	
(n)			1	1		24		
CCI								
CCI		1	1		1	1	1	
CCI								
D: (1			V		N			
Dispense study			X		X			
DTE server ()	77	X 7	T					
PIE assessment (r)	X	X	X V	37		NZ		T
AE assessment			X	X	X	X	X	X

Footnotes are on the next page.

1AK-020	
Study No. TAK-020-1001	Page 88 of 101
Protocol Incorporating Amendment No. 4.0	27 March 2017

(a) Conduct procedures for subjects discontinued early. The PK sample collection should be collected at the Early Termination Visit, if possible. For example, collect samples if early withdrawal is due to an AE, and/or if several hours elapsed since last blood draw].

(b) All subjects will return to the unit and complete Hematology and Serum Chemistry tests, vital signs, concomitant medications, and AE assessment.

(c) The physical examination can be conducted within 24 hours prior to study drug administration.

(d) Vital signs (oral temperature, sitting pulse, and blood pressure) will be collected at Screening and Check-in (Day -1) and on Day 1 at predose (0 hours) and 1, 4, 12, 24 hours postdose, then twice daily until Study Exit (Day 10) or Early Termination and once during the Follow-up visit.

(e) Height will only be collected at Screening.

TATZ 030

(f) Record all medications (other than study drug) from Screening and throughout the study.

(g) Clinical laboratory tests (hematology, serum chemistries, and urinalysis) will be collected at Screening, Day -1, Days 2, 3, 5, 8 and prior to check-out (Day 10) or Early Termination. Laboratory samples will be taken following a minimum 10-hour overnight fast

(h) Pregnancy test (hCG) will be performed for all female subjects.

(i) Triplicate 12-lead ECGs printed in standard format, will be collected at Screening, Check-in (Day -1), Day 1 predose (0 hours) and at 1, 4, 12, and 24 hours postdose, Days 3, 5, 9, 10 at predose (0 hours) or Early Termination. For ad hoc ECGs, as required, see Section 9.1.11.

(j) Telemetry will be performed approximately 2 hours predose until 12 hours postdose on Days 1 and 9 only. Ten (10) sec triplicate ECGs will be extracted at PK time-points for manual reading and precise ECG reading including QT interval measurement.

(k) One blood sample (6 mL) will be collected prior to dosing on Day 1.

(I) Two whole blood samples (2.5 mL per sample) will be collected at predose on Days 1, 3 and 9.

(m) Blood samples for PK analysis will be collected at predose on Day 1 (within 30 minutes prior to dosing) and at 0.25, 0.5, 0.75, 1, 2, 3, 4, 6, 8, 10, 12, 16, 24, 36, and 48 hours postdose and at predose on Day 9 (within 30 minutes prior to dosing) and at 0.25, 0.5, 0.75, 1, 2, 3, 4, 6, 8, 10, 12, 16, and 24 hours postdose.

(n) Urine samples for PK analysis will be collected on Day 1 and Day 9 at predose (-12-0), and 0-6, 6-12, 12-24 hour postdose intervals

(r) PTEs will be collected from signing of informed consent up until dosing on Day 1

(s) Hematology and Serum Chemistry only.

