#### Study Schematic for Part 2 (MRD)

Screening	Check-in	Dose	Washout	Dose	Check-out	Follow-up (a)
Day -28 to -2	Day -1	Day 1	Day 2	Days 3-9	Day 10	Day 17 (±2)

(a) All subjects will return to the unit and complete hematology, serum chemistry, renal biomarkers and pharmacodynamic (PD) tests, vital signs, concomitant medications, and adverse event (AE) assessment.

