## **Study Schematic for Part 2**

Screening	Check-in	Dose	Washout	Dose	Check-out	Follow-up (a)
Day -28 to -2	Day -1	Day 1	Day 2	Days 3-9	Day 10	Day 17 (±2)

(a) All subjects will return to the unit and complete hematology, serum chemistry, renal biomarkers and pharmacodynamic tests, vital signs, concomitant medications, and AE assessment.

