## 9.1.8 Procedures for Clinical Laboratory Samples

All samples will be collected in accordance with acceptable laboratory procedures. The maximum volume of blood at any single visit is approximately 140 mL, and the approximate total volume of blood for the study is 300 mL for Part 1 and 413 mL for Part 2. Laboratory samples will be taken following a minimum 10-hour overnight fast on the days stipulated in the Schedule of Study Procedures Appendix A.

Table 9.a lists the tests that will be obtained for each laboratory specimen.

Hematology	Serum Chemistry		Urinalysis
RBC WBC with differential [both % and absolute count] Hemoglobin Hematocrit Platelets prothrombin time /INR aPTT Fibrinogen	Alanine aminotransferase         Albumin         Albumin: Globulin ratio         Alkaline phosphatase         Amylase         Aspartate aminotransferase         Total bilirubin         Total protein         C-reactive protein         Cholesterol         Creatinine (eGFR) [8]         Cystatin -C         Blood urea nitrogen         Creatine kinase         γ-Glutamyl transferase         Glutamate dehydrogenase         Potassium         Sodium         Glucose         Chloride         Quantitative IgA, IgG and         Triglycerides         Bicarbonate         Calcium	e IgM	pH Specific gravity Protein Glucose Blood Nitrite Renal Biomarkers: Kidney Injury Molecule-1 (KIM-1)/ TIM-1 (T Cell Immunoglobulin Mucin 1) Cystatin C Neutrophil Gelatinase-Associated Lipocalin (NGAL) Urine Albumin Urine Protein Microscopic Analysis (performed only if urine evaluations are abnormal): RBC/high power field WBC/high power field Epithelial cells, casts etc
Diagnostic Screening:	Lipase		
Serum		Urine	
Henatitis nanel_including H	IBsAg and anti-HCV	Drug screen including ample	tamines harbiturates
(and/or HCV RNA), HIV-1 and HIV-2 screening, TB screening (QuantiFERON)		benzodiazepines, cannabinoida and cotinine.	s, cocaine, opiates, alcohol,
Female subjects only:			
hCG (for pregnancy) FSH if menopause is suspec	eted		

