## 9.3.3 Follow-up Visit/Telephone Call

Subjects with unresolved SAEs, CS laboratory abnormalities, ECG or physical exam findings or at the PI's discretion should be seen for a Follow-up visit on Day 14 ( $\pm 2$  days) in Part 1 for appropriate repeat procedure(s). A Follow-up phone call will be made to all other subjects on Day 14 ( $\pm 2$  days) in Part 1 for an assessment of AEs and concomitant medications. In Part 2, all subjects will return the clinical site on Day 17 ( $\pm 2$  days) for laboratory tests (Hematology, Serum Chemistry, Urinary renal biomarkers, and PD tests), assessment of vital signs, AEs and concomitant medications.

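### The visible Part 2 schedule leaves out the Day 17 renal biomarkers that Section 9.3.3 requires; separately, the SAP's 7-day rule keeps a nominal Day 17 visit out of the descriptive laboratory tables

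*Protocol*

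**What the plan says.** Three places in the current protocol put renal biomarkers on the Part 2 Follow-up visit for all subjects. Section 9.3.3 brings everyone back "for laboratory tests (Hematology, Serum Chemistry, Urinary renal biomarkers, and PD tests), assessment of vital signs, AEs and concomitant medications". Footnote (a) to the Part 2 schematic in the Study Summary has them "complete hematology, serum chemistry, renal biomarkers and pharmacodynamic (PD) tests, vital signs, concomitant medications, and adverse event (AE) assessment". Footnote (a) to the Part 2 schematic in Figure 6.a says: "All subjects will return to the unit and complete hematology, serum chemistry, renal biomarkers and pharmacodynamic tests, vital signs, concomitant medications, and AE assessment".

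Appendix A Part 2 gives a shorter list. The Follow-up cell of the clinical laboratory row carries footnote (s): "s) Hematology and Serum Chemistry only". Footnote (b), on the same visit, reads "b) All subjects will return to the unit and complete Hematology and Serum Chemistry tests, vital signs, concomitant medications, and AE assessment". Footnote (g) names the three groups of clinical laboratory tests and their days: "hematology, serum chemistries, and urinalysis) will be collected at Screening, Day -1, Days 2, 3, 5, 8 and prior to check-out (Day 10", with Early Termination as the alternative to Day 10. Table 9.a prints the renal biomarkers in the urinalysis column: KIM-1, then "Cystatin C Neutrophil Gelatinase-Associated Lipocalin (NGAL) Urine Albumin Urine Protein". Section 9.1.8 points to the schedule for sampling days: "Laboratory samples will be taken following a minimum 10-hour overnight fast on the days stipulated in the Schedule of Study Procedures Appendix A".

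SAP Section 7.11.2 limits the descriptive laboratory tables to scheduled results no later than 7 days after the final dose. It gives renal biomarkers a summary of their own without saying whether that limit applies to them. It counts MAVs from every postdose result. SAP Table 4.a (Part 2 footnote (a)) and SAP Appendix A (Part 2 footnotes (b) and (s)) carry the shorter Day 17 list. The SAP's reference list cites Protocol Amendment 3.

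**The concern.** Protocol Section 6.2 treats kidney changes as irreversible, because reversibility was not shown in animals, and undertakes to monitor markers of kidney injury. The routine urinary samples at or before Day 10 are taken during dosing or about 24 hours after the last dose. Day 17 is the one planned look at whether a urinary change appears late or persists. A site that plans the visit from Appendix A could omit that urine collection, and the exploratory comparison in Section 13.1.5.5 would lose a time point.

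The second part concerns results that are collected. If the by-visit laboratory tables exclude most Follow-up results, a modest Day 17 shift would be visible only in listings. The MAV table does not fill that gap. SAP Appendix B counts creatinine only above 2.0 mg/dL and has no criterion for serum cystatin C, eGFR or the urinary markers.

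**Working it through.** **Step 1. Day 17 content, text against text (all current wording).**

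| Place | Renal biomarkers on Day 17? |
|---|---|
| Protocol 9.3.3 | Yes, all Part 2 subjects |
| Study Summary, Part 2 schematic (a) | Yes, all subjects |
| Figure 6.a, Part 2 schematic (a) | Yes, all subjects |
| Protocol Appendix A Part 2, footnote (s) | No: two test groups, with the word only |
| Protocol Appendix A Part 2, footnote (b) | Not mentioned |
| SAP Table 4.a (a); SAP Appendix A Part 2 (b), (s) | Same shorter list |

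**Step 2. Does (s) exclude the urinary markers?** Footnote (g) keeps urinalysis apart from hematology and serum chemistry, and schedules it at Screening and on Days -1, 2, 3, 5, 8 and 10, not Day 17. Table 9.a places the renal biomarkers in the urinalysis column. Restricting the row to the other two groups therefore leaves them out. Footnote (b) is not a complete list of the visit, so the conflict rests on (s).

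**Step 3. What remains on Day 17 if (s) is followed.** Serum creatinine with eGFR, serum cystatin C and blood urea nitrogen are serum chemistry and are still drawn. Verified clinically significant abnormalities are still followed under Section 9.1.8. The renal dose-limiting toxicity in Table 6.a uses serum creatinine or eGFR only. The adverse-event review in Section 6.1.1 runs to Day 10 discharge. What can be lost is mainly the routine urine sample in subjects with no clinically significant finding on Day 10.

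**Step 4. Day arithmetic for the SAP rule.** The last Part 2 dose is on Day 9 (Section 7.4). Days after last dose = visit day − 9. The SAP's adverse-event definition (Section 7.11.1) adds 1, so both counts are shown.

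| Visit day | Difference | ≤7? | With +1 | ≤7? |
|---|---|---|---|---|
| 15 | 6 | in | 7 | in |
| 16 | 7 | in | 8 | out |
| 17 | 8 | out | 9 | out |
| 18 | 9 | out | 10 | out |
| 19 | 10 | out | 11 | out |

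Nominal Day 17 is out on either count. The rule drops 3 of the 5 permitted days, or 4 of 5 with +1.

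**Step 5. Subjects concerned.** Cohorts 5-7: 3 × 8 = 24 subjects, 3 × 6 = 18 on TAK-020. All of Part 2: 7 × 8 = 56 subjects, 7 × 6 = 42 on TAK-020.

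**Step 6. Exposure, for context only (Section 6.2).** Rat kidney toxicity was seen at a total AUC of 2030 ng·h/mL. With 98.0% protein binding, 2030 × 0.020 = 40.6 ng·h/mL unbound. The stated human maximum is 19.9 unbound, and 19.9 / 40.6 = 0.49. On total exposure, 1808 / 2030 = 0.89. The rat figure comes from 4 weeks of dosing and Part 2 gives at most 8 doses, so this is background and not an effect of the footnote.

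**The case against.** *Redaction.* Some Part 2 rows of Appendix A are blacked out, and footnotes (o) to (q) are not visible. A separate renal-biomarker row could be among them. This stands as a limit on certainty. It is unlikely, because renal biomarkers are unredacted elsewhere in the protocol and Table 9.a lists them with the clinical laboratory tests.

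*Scope of (s).* The footnote qualifies one row. Section 9.3.3 also counts PD tests as Day 17 laboratory work, and neither (b) nor (s) mentions them, so (s) is not a full list of the visit. That is fair. Even so, the row it governs is where Table 9.a would place these markers, and its wording is restrictive.

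*Precedence.* A reader might infer that Appendix A overrides Section 9.3.3. The documents do not say so. Section 9.3 says where the schedule is shown, and the Section 9.1.8 sentence sets fasting and refers to the scheduled days. Three explicit statements favor collection, and the single site may well follow them. Harm needs the site to follow the footnote instead.

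*The SAP rule.* A 7-day window is clear and self-consistent. Protocol Section 13.1 leaves analysis detail to the SAP, Section 13.1.5.2 does not require every visit to be tabulated, and PK washout is expected within 24 hours. This stands: the rule contradicts no protocol text.

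*Cause.* Because the SAP cites Amendment 3, a reader might infer that an outdated source explains its shorter list. The Amendment 4 change list names only PD biomarkers as the Day 17 addition, so that cause is not shown.

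**Conclusion.** Two conclusions of different standing.

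(1) Footnote (s) is wrong as written, with footnote (b) silent on the same point. The impact is limited. In the worst case, one routine urinary sample per subject is lost, and the last routine urinary value falls about 1 day after the last dose instead of 6 to 10 days. This assumes that no hidden row schedules the markers and that the site follows the footnote. The number who can still benefit (up to 24, of whom 18 on TAK-020) assumes that Cohorts 1-4 are complete, as Section 6.2 suggests.

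(2) The SAP cut-off is a cheap improvement, not an error. It affects the descriptive tables for up to 56 Part 2 subjects (42 on TAK-020). Whether it reaches the renal-biomarker summary is unstated.

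A reader might go further and infer that Day 17 has no renal check, or that the primary safety endpoint or the stopping rules are compromised. The documents do not support that. Serum renal tests are still drawn on Day 17, MAV counts use all postdose results, listings are complete, and neither the renal dose-limiting toxicity nor the escalation review depends on the urinary markers.

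**What to change.** Protocol: add urinary renal biomarkers to Appendix A Part 2 footnotes (b) and (s), to match Section 9.3.3. Leave the redacted rows as they are.

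SAP: make the matching edits in Table 4.a (Part 2 footnote (a)) and Appendix A (Part 2 footnotes (b) and (s)), and update the protocol reference to Amendment 4. In Section 7.11.2, add one sentence saying that the scheduled Part 2 Follow-up visit (Day 17 ±2) is summarized as its own post-treatment row for laboratory tests and renal biomarkers.

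Cost: a few footnote edits, one reference and one sentence. There is no new visit and no added blood volume, since Section 9.3.3 already requires the urine sample at a visit all Part 2 subjects attend. The downside is one extra table row that mixes visits 6 to 10 days after the last dose.

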# Appendix B Responsibilities of the Investigator

Clinical research studies sponsored by the sponsor are subject to ICH GCP and all the applicable local laws and regulations. The responsibilities imposed on investigators by the FDA are summarized in the "Statement of Investigator" (Form FDA 1572), which must be completed and signed before the investigator may participate in this study.

The investigator agrees to assume the following responsibilities by signing a Form FDA 1572:

- 1. Conduct the study in accordance with the protocol.
- 2. Personally conduct or supervise the staff that will assist in the protocol.
- 3. Ensure that study related procedures, including study specific (nonroutine/nonstandard panel) screening assessments, are NOT performed on potential subjects, prior to the receipt of written approval from relevant governing bodies/authorities.
- 4. Ensure that all colleagues and employees assisting in the conduct of the study are informed of these obligations.
- 5. Secure prior approval of the study and any changes by an appropriate IRB/IEC that conform to 21 Code of Federal Regulations (CFR) Part 56 ICH, and local regulatory requirements.
- 6. Ensure that the IRB/IEC will be responsible for initial review, continuing review, and approval of the protocol. Promptly report to the IRB/IEC all changes in research activity and all anticipated risks to subjects. Make at least yearly reports on the progress of the study to the IRB/IEC, and issue a final report within 3 months of study completion.
- 7. Ensure that requirements for informed consent, as outlined in 21 CFR Part 50 ICH and local regulations, are met.
- 8. Obtain valid informed consent from each subject who participates in the study, and document the date of consent in the subject's medical chart. Valid informed consent is the most current version approved by the IRB/IEC. Each informed consent form should contain a subject authorization section that describes the uses and disclosures of a subject's personal information (including personal health information) that will take place in connection with the study. If an informed consent form does not include such a subject authorization, then the investigator must obtain a separate subject authorization form from each subject or the subject's legally acceptable representative.
- 9. Prepare and maintain adequate case histories of all persons entered into the study, including eCRFs, hospital records, laboratory results, etc, and maintain these data for a minimum of 2 years following notification by the sponsor that all investigations have been discontinued or that the regulatory authority has approved the marketing application. The investigator should contact and receive written approval from the sponsor before disposing of any such documents.
- 10. Allow possible inspection and copying by the regulatory authority of GCP-specified essential documents.

TAK-020	
Study No. TAK-020-1001	Page 90 of 101
Protocol Incorporating Amendment No. 4.0	27 March 2017

- 11. Maintain current records of the receipt, administration, and disposition of sponsor-supplied drugs, and return all unused sponsor-supplied drugs to the sponsor.
- 12. Report adverse reactions to the sponsor promptly. In the event of an SAE, notify the sponsor within 24 hours.

# Appendix C Elements of the Subject Informed Consent

In seeking informed consent, the following information shall be provided to each subject:

- 1. A statement that the study involves research.
- 2. An explanation of the purposes of the research.
- 3. The expected duration of the subject's participation.
- 4. A description of the procedures to be followed, including invasive procedures.
- 5. The identification of any procedures that are experimental.
- 6. The estimated number of subjects involved in the study.
- 7. A description of the subject's responsibilities.
- 8. A description of the conduct of the study.
- 9. A statement describing the treatment(s) and the probability for random assignment to each treatment.
- 10. A description of the possible side effects of the treatment that the subject may receive.
- 11. A description of any reasonably foreseeable risks or discomforts to the subject and, when applicable, to an embryo, fetus, or nursing infant.
- 12. A description of any benefits to the subject or to others that reasonably may be expected from the research. When there is no intended clinical benefit to the subject, the subject should be made aware of this.
- 13. Disclosures of appropriate alternative procedures or courses of treatment, if any, that might be advantageous to the subject and their important potential risks and benefits.
- 14. A statement describing the extent to which confidentiality of records identifying the subject will be maintained, and a note of the possibility that regulatory agencies, auditor(s), IRB/IEC, and the monitor may inspect the records. By signing a written informed consent form, the subject or the subject's legally acceptable representative is authorizing such access.
- 15. For research involving more than minimal risk, an explanation as to whether any compensation and an explanation as to whether any medical treatments are available if injury occurs and, if so, what they consist of or where further information may be obtained.
- 16. The anticipated prorated payment(s), if any, to the subject for participating in the study.
- 17. The anticipated expenses, if any, to the subject for participating in the study.
- 18. An explanation of whom to contact for answers to pertinent questions about the research (investigator), subject's rights, and IRB/IEC and whom to contact in the event of a research-related injury to the subject.
- 19. A statement that participation is voluntary, that refusal to participate will involve no penalty or loss of benefits to which the subject otherwise is entitled, and that the subject may discontinue

participation at any time without penalty or loss of benefits to which the subject is otherwise entitled.

- 20. The consequences of a subject's decision to withdraw from the research and procedures for orderly termination of participation by the subject.
- 21. A statement that the subject or the subject's legally acceptable representative will be informed in a timely manner if information becomes available that may be relevant to the subject's willingness to continue participation in the study.
- 22. A statement that results of PGx analysis will not be disclosed to an individual, unless prevailing laws require the sponsor to do so.
- 23. The foreseeable circumstances or reasons under which the subject's participation in the study may be terminated.
- 24. A written subject authorization (either contained within the informed consent form or provided as a separate document) describing to the subject the contemplated and permissible uses and disclosures of the subject's personal information (including personal health information) for purposes of conducting the study. The subject authorization must contain the following statements regarding the uses and disclosures of the subject's personal information:
  - a) that personal information (including personal health information) may be processed by or transferred to other parties in other countries for clinical research and safety reporting purposes, including, without limitation, to the following: (1) Takeda, its affiliates, and licensing partners; (2) business partners assisting Takeda, its affiliates, and licensing partners; (3) regulatory agencies and other health authorities; and (4) IRBs/IECs;
  - b) it is possible that personal information (including personal health information) may be processed and transferred to countries that do not have data protection laws that offer subjects the same level of protection as the data protection laws within this country; however, Takeda will make every effort to keep your personal information confidential, and your name will not be disclosed outside the clinic unless required by law;
  - c) that personal information (including personal health information) may be added to Takeda's research databases for purposes of developing a better understanding of the safety and effectiveness of the study medication(s), studying other therapies for patients, developing a better understanding of disease, and improving the efficiency of future clinical studies;
  - d) that subjects agree not to restrict the use and disclosure of their personal information (including personal health information) upon withdrawal from the study to the extent that the restricted use or disclosure of such information may impact the scientific integrity of the research; and
  - e) that the subject's identity will remain confidential in the event that study results are published.

TAK-020	
Study No. TAK-020-1001	Page 93 of 101
Protocol Incorporating Amendment No. 4.0	27 March 2017

- 25. Female subjects of childbearing potential (eg, nonsterilized, premenopausal female subjects) who are sexually active must use adequate contraception (as defined in the informed consent) from Screening and throughout the duration of the study, and until the next menstrual period or 30 days after last dose, whichever is first. Regular pregnancy tests will be performed throughout the study for all female subjects. If a subject is found to be pregnant during study, study medication will be discontinued and the investigator will offer the subject the choice to receive unblinded treatment information.
- 26. Male subjects must use adequate contraception (as defined in the informed consent) from Screening, throughout the duration of the study and for 12 weeks after last dose. If the partner or wife of the subject is found to be pregnant during the study, the investigator will offer the subject the choice to receive unblinded treatment information.
- 27. A statement that clinical trial information from this trial will be publicly disclosed in a publicly accessible website, such as www.ClinicalTrials.gov.

